7.9.3 Vital Signs

The following vital signs will be summarized by treatment group and visit.

- Sitting systolic and diastolic blood pressure (mm Hg)*
- Heart rate (bpm)*
- Weight (kg)*
- Waist circumference (cm)*

*Also evaluated as an efficacy parameter.

Vital signs data and changes from baseline in vital signs will be summarized by visit using standard descriptive statistics for the SAF population. The baseline value will be defined as last scheduled or unscheduled value collected prior to the first dose of treatment. For analysis by visit, analysis windowing as described in Section 6.1 will be utilized for each scheduled visit such that unscheduled visits will also be considered.

Mean change in weight from baseline with standard error bars will be plotted for each treatment group by visit in the SAF population.

7.9.4 Electrocardiograms

Electrocardiogram (ECG) measurements and changes from baseline in ECG measurements will be summarized by visit using standard descriptive statistics for the SAF population. If a subject has both central and local ECGs for a given time point, the local values will be used for analysis. Summary statistics for the following parameters will be presented: ECG mean heart rate, PR interval, QRS duration, QT interval, QTcB interval, QTcF interval, RR interval. Number and percentage of subjects with atrial fibrillation, sinus rhythm, or other rhythm will be presented by visit.

7.9.5 Physical Examination

Physical examination results (normal or abnormal) and details of abnormalities will be listed for each subject.

For each physical examination body system, the number and percentage of subjects with abnormalities at baseline and post-baseline will be summarized by treatment group for the SAF population.

The distribution of edema grades reported at baseline and at each post-baseline visit will be presented by treatment group.

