2 BACKGROUND AND RATIONALE FOR THE STUDY

2.1 Background

MSDC-0602K is a novel insulin sensitizer that interacts with a newly identified mitochondrial target (mTOT, **mitochondrial Target Of the Thiazolidinediones**), while sparing direct activation of the PPAR γ receptor believed to be associated with side effects of volume expansion and weight gain related to the first generation of insulin sensitizers which were marketed as PPAR γ agonists ([1-3](#)). As an mTOT modulating insulin sensitizer, MSDC-0602K has a favorable pharmacological profile to treat fatty liver disease including non-alcoholic steatohepatitis (NASH). The effects of MSDC-0602K have been evaluated in two animal models of fatty liver disease. In the first model, C57B1/6J mice were fed a diet providing 60% of its calories as fat for 10 weeks (C57 DIO mice) and then administered a high fat diet containing either no drug or MSDC-0602K 30 mg/kg for 2 to 4 weeks. Treatment of these mice resulted in a number of positive effects associated with the insulin-sensitizing pharmacology, including a complete clearance of fat from the liver once the high fat diet was removed. Consistent with the proposed mechanism of action, MSDC-0602K treatment reduced the activation of mTOR in the liver and resulted in changes that favored lipid oxidation over lipid storage ([4](#)). Since the C57 DIO mouse model does not develop liver lesions that are representative of NASH, similar studies were repeated in C57 mice fed a diet containing a high content of trans fat (40% of calories, mainly trans-oleic and trans-linoleic acids) together with cholesterol (2%) and fructose (22%). This diet produces scarring of the liver and a liver pathology with ballooning that is characteristic of NASH. Treatment of these mice with MSDC-0602K after 4 weeks of this diet through 16 weeks of age produced a significant reduction in the portal tract pathology even though the mice were retained on the diet throughout the 16 week period. These data suggest that MSDC-0602K should be effective in the treatment of NASH.

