7.2 Physical Examinations

A complete physical examination will be performed at Screening and at the Follow-Up Visit (Day 374, Study Visit 8); a limited physical examination will be performed at all other study visits (Study Visits 1-7). Information regarding body weight, waist circumference and assessment for the presence of edema will be collected at all study visits and height will be recorded only at Screening. Subjects are to be weighed in similar attire without shoes on the same scale at each visit. Measure waist circumference as follows:

Locate the lowest rib and the iliac crest. Place the tape measure evenly around the bare abdomen at the midpoint between the lowest rib and the iliac crest. Read the tape measure and record the waist circumference in centimeters.

The complete physical examination will be comprised of the following general categories of parameters: General Appearance, Dermatological, Head Ears Eyes Nose and Throat (HEENT)/Neck, Pulmonary, Cardiovascular, Gastro-Intestinal, Neurological, Extremities, Lymphatic, and Other.

The limited physical examination will be comprised of at least the following categories of parameters: Pulmonary, Cardiovascular, and Extremities. The presence or absence of edema will be recorded as “yes“ or “no“ at each complete and limited physical examination. If “yes,“ a grade will be recorded for the edema. Peripheral edema will be assessed as follows:

Place your index finger over the participant's tibia, 10 cm above the lateral malleolus. Exert pressure for 5 seconds. Any depression that does not resume its original contour almost immediately is a sign of pitting edema. Record if there is no edema observed. The following scale should be used to grade any edema that is observed.

Grade **Physical Characteristics**

- 1+ No visible change in shape of the extremity, pitting \leq 2 mm, pit disappears rapidly
- 2+ No marked change in the shape of the extremity, 2 mm < pitting \leq 5 mm, pit usually disappears in 10-15 seconds
- 3+ Noticeably swollen extremity, 5 mm < pitting \leq 10 mm, pit may persist for about a minute
- 4+ Very swollen and distorted extremity, very deep pit > 10 mm, pit may persist 2 - 5 minutes

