9.1.1 Adverse Event Definitions

An AE is any untoward medical occurrence in a subject or trial subject that is administered a drug or biologic (medicinal product) or that is using a medical device; the event does not necessarily have a causal relationship with that treatment or usage. Adverse events include the following:

- All suspected adverse reactions
- All reactions from overdose, abuse, withdrawal, sensitivity, or toxicity.
- Apparently unrelated illnesses, including the worsening of a preexisting illness
- Injury or accidents. Note that if a medical condition is known to have caused the injury or accident (e.g., a fall secondary to dizziness or orthostasis), the medical condition (dizziness) and the accident (fall) should be reported as 2 separate adverse events. The outcome of the accident (e.g., hip fracture secondary to the fall) should be recorded in source documents.
- Abnormalities in physiological testing or physical examination findings that require clinical intervention or further investigation (beyond ordering a repeat test).
- Laboratory abnormalities that require clinical intervention or further investigation (beyond ordering a repeat test) unless they are associated with an already reported clinical event. Laboratory abnormalities associated with a clinical event (e.g., elevated liver enzymes in a subject with jaundice) should be captured in the source documents.

Each adverse event is to be classified by the Investigator as serious or non-serious. This classification of the gravity of the event determines the reporting procedures to be followed.

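### SAP 7.9.5 tabulates graded edema visit by visit and plans no count of subjects with new or worsened edema from those examinations

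*SAP*

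**What the plan says.** Protocol 7.2 makes edema a systematic measurement: "Information regarding body weight, waist circumference and assessment for the presence of edema will be collected at all study visits". A yes/no finding is recorded, edema that is present is graded 1+ to 4+, and the finger-pressure test is standardised.

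SAP 7.9.5 plans three outputs that can carry edema:

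- **Edema grades.** "The distribution of edema grades reported at baseline and at each post-baseline visit will be presented by treatment group".
- **Body systems.** For each system, "the number and percentage of subjects with abnormalities at baseline and post-baseline will be summarized by treatment group for the SAF population". Extremities is an examined category under Protocol 7.2.
- **Listings.** "Physical examination results (normal or abnormal) and details of abnormalities will be listed for each subject".

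SAP 7.9.1 separately counts subjects with each treatment-emergent adverse event by preferred term and arm. Each subject counts once per term, and earlier events that worsen on treatment are included. Among the kinds of adverse event named in Protocol 9.1.1 are "Abnormalities in physiological testing or physical examination findings that require clinical intervention or further investigation (beyond ordering a repeat test").

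Edema is not among the safety variables of SAP 3.4. Protocol 11.3.3.2 says only that the physical examination will be summarised descriptively.

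**The concern.** Protocol 2.1 presents the drug as sparing the receptor believed to cause "side effects of volume expansion and weight gain related to the first generation of insulin sensitizers". Protocol 2.2.2 names edema among the effects of other insulin sensitizers that were not seen in the chronic animal studies. Protocol 2.3.1 reports no clinically meaningful difference from placebo in edema in the earlier four-week-treatment Phase 2a study. A 12-month trial with graded examinations at every visit is well placed to test that claim. The natural question is how many subjects in each arm developed edema or got worse.

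A series of visit-by-visit distributions does not answer it. Each column is a prevalence among those examined at that visit, not a count of subjects affected since baseline. The SAP uses more informative summaries elsewhere: baseline-to-visit shift tables for hematology and chemistry (7.9.2), and subjects with any event through 14 days after last dose for severe hypoglycemia and fractures (7.9.7, 7.9.8).

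**Working it through.** The plan gives no edema rate, duration or target, so it has no figure of its own to reproduce. Its power statement concerns the histological endpoint and has no bearing here.

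**What each planned output can show**

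| Output | Edema-specific | Graded | New or worsened per subject, by arm |
|---|---|---|---|
| Grade distribution per visit (SAP 7.9.5) | yes | yes | no |
| Body-system abnormalities (SAP 7.9.5) | no | no | no |
| Subject listings (SAP 7.9.5) | can be | can be | no count by arm |
| Treatment-emergent adverse events (SAP 7.9.1) | yes, by preferred term | by event severity, not examination grade | yes, if recorded as an adverse event |

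**Why the visit columns do not give incidence**

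1. Suppose k subjects have edema at baseline and k at a later visit. They may be the same subjects (0 new cases) or all different (k new cases). The column totals cannot tell these apart.
2. A subject whose edema resolves returns to the no-edema row.
3. A subject who stops drug leaves later columns altogether. The safety set uses assessments through 14 days after last dose (SAP 5.3), and the default denominator is subjects with a non-missing value (SAP 7.1).
4. When a scheduled and an unscheduled result fall under the same post-baseline visit, the scheduled one is used (SAP 6.1). Edema found only at the unscheduled examination is then not shown.

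**Possible size (all rates and durations assumed)**

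Assume that 12% of an arm has one episode, that onset is uniform over 360 days, and that there is no baseline edema and no dropout. Visits are at Days 30, 60, 90, 180, 270 and 360. For an episode of L days, prevalence at Day t is 12% × min(t, L)/360. The proportion ever observed is 12% × (days of onset that some visit catches)/360.

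- **L = 60.** Day 30: 12 × 30/360 = 1%. Each later visit: 12 × 60/360 = 2%. Mean: (1 + 5 × 2)/6 = 1.8%. Onsets caught: days 0-90, 120-180, 210-270 and 300-360, which is 90 + 60 + 60 + 60 = 270 days. Ever observed: 12 × 270/360 = 9.0%.
- **L = 90.** Days 30 and 60: 1% and 2%. Day 90 onward: 3%. Mean: (1 + 2 + 4 × 3)/6 = 2.5%. All 360 onset days are caught, so 12% are ever observed.
- **Persistent edema.** Day 360: 12 × 360/360 = 12%, equal to the proportion ever affected.

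Adding the Day 374 visit leaves the proportions ever observed unchanged, because the Day 360 visit already catches those onsets.

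**Difference between arms**

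Assume that 15% against 5% of subjects are ever affected, over seven post-baseline examinations, with onset uniform over visits and episodes lasting d visits. The largest gap at one visit is 10 points × d/7: 1.4 points for d = 1, 2.9 for d = 2, 4.3 for d = 3, and the full 10 for edema that persists to the last visit (d = 7). With 380/4 = 95 subjects per arm and d = 2, a single column shows about 95 × 0.15 × 2/7 = 4 subjects against 95 × 0.05 × 2/7 = 1. The subjects ever affected number about 95 × 0.15 = 14 and 95 × 0.05 = 5.

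**The case against.** A reader might infer that edema incidence goes unreported, or that the plan cannot give treatment-emergent edema by arm. The documents do not support that. SAP 7.9.1 counts subjects by preferred term, includes worsening, and tabulates events by maximum severity and those leading to discontinuation or interruption. Edema that needs treatment meets the intervention condition in Protocol 9.1.1. Edema for which the investigator stops drug fits the adverse event ground in Protocol 6.3. Most of the consequential cases should therefore reach the event tables. The list in Protocol 9.1.1 is also inclusive rather than exhaustive, and Protocol 9.1 asks for all observed and spontaneously reported events, so even a mild complaint of swelling may be recorded. This objection stands. What it leaves open is low-grade edema needing no action, which may or may not become an event.

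A reader might also take a four- to fivefold understatement as established (9.0/1.8 and 12/2.5 are both about 5). It is not, because it rests on short episodes that resolve. If edema persists on daily dosing and subjects stay in the study, the last visit shows it in full. With equal duration and follow-up across arms, each column also keeps the ratio to placebo (3 to 1 in the example). What shrinks is the absolute difference and the number of subjects behind it.

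Finally, the trial's stated aim is preliminary safety. Weight change (SAP 7.9.3) and adjudicated heart-failure admissions (SAP 7.9.6) also bear on fluid retention. They are useful context but do not count subjects with edema.

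**Conclusion.** The gap is real and small. The systematically graded edema examinations are summarised only as distributions at each visit, and no number and percentage of subjects with new or worsened edema is planned from them. The event tables give that count for edema recorded as an adverse event and may miss low-grade edema.

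Per-visit prevalence may understate treatment-emergent edema, but by how much cannot be known from the documents. The illustration runs from 1-3% per visit against 9-12% ever observed (12% incidence, 60- to 90-day episodes) to no understatement at the last visit (persistent edema, no dropout). The absence of the summary rests on the text alone. Every figure for its size rests on assumed rates and durations. The point touches neither the primary analysis nor the conduct of the trial.

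**What to change.** Add to SAP 7.9.5, for the safety analysis set and by arm:

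1. A shift table of baseline edema grade (none, 1+ to 4+) against worst post-baseline grade, using all scheduled and unscheduled examinations through 14 days after last dose.
2. The number and percentage of subjects with new edema or a worsening of at least one grade.

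Keep the visit-by-visit distribution as the display of time course. Any difference from placebo with a 95% confidence interval should be labelled descriptive, in keeping with SAP 7.9.1, which plans no statistical comparison of treatment-emergent events.

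The cost is one extra table from grades already collected. No new data are needed, and no clinical rule changes.

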7.9.6 Major Adverse Cardiovascular Events and Liver Events

A Clinical Events Committee (CEC) will adjudicate Major Adverse Cardiovascular Events (MACE), which are defined as death, adjudicated non-fatal MI or USA hospitalization, adjudicated hospital admission for HF, or adjudicated non-fatal ischemic stroke. Time from baseline to occurrence of first event will be computed in days. Subjects without an event will be censored at the earlier of the end of the time period of interest and the last contact date.

Time to first MACE through 14 days after last dose of study treatment will be presented as number of events with Kaplan-Meier estimates of the cumulative risk of event. Hazard ratios and corresponding 95% confidence intervals comparing each active treatment group to placebo will be estimated from a Cox proportional hazards model including a factor for treatment group; and the model will be stratified by randomization stratification factors (presence of diabetes mellitus, Vitamin E \geq 400 IU, and baseline fibrosis F1 versus F2/F3) if the number of events permits. Treatment groups will be compared using a log-rank test.

Similarly, time to first MACE or adjudicated liver event (ascites, hepatic encephalopathy, variceal hemorrhage, hepatocellular carcinoma, or liver transplant) through 14 days after last dose of study treatment will be analyzed and presented.

Results will also be provided for each component of these composite events. For non-fatal events, subjects who die before the time point of interest and who did not reach the event of interest before death will be censored on the day of death. Results will be presented through 14 days after last dose of study treatment for:

- Time to death
- Time to first adjudicated non-fatal MI
- Time to first adjudicated USA hospitalization
- Time to first adjudicated hospital admission for HF
- Time to first adjudicated non-fatal ischemic stroke
- Time to first adjudicated liver event

In addition, deaths will be presented in a listing including investigator-reported data and the adjudicated primary cause of death.

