6.3 Discontinuation of Study Drug and Study Termination

Subjects are free to discontinue participation in the study at any time and for any reason without prejudice to future medical care; however, prior to randomization, it should be made clear to potential subjects that early withdrawal from the study including loss to follow up can be extremely damaging to the scientific research and may pose some risk to the subject. If a subject withdraws consent to be treated with study drug prior to receiving any dose of study drug, the subject should be discontinued from the study. Once a subject has been randomized, the investigator will make every reasonable effort to keep the subject in the study.

Subjects may withdraw from study for the following reasons:

- Withdrawal of informed consent: A subject should be considered to have withdrawn consent when the subject no longer wishes to participate in any aspect of the study, and

does not want any further assessments, visits, or contact. A subject's refusal to participate in specific aspects of the study, such as a refusal to continue taking study drug or to provide blood samples, will NOT constitute withdrawal of consent. Investigators should make every effort to facilitate the subject's continued participation in remaining aspects of the study.

- Subject is lost to follow-up: A subject will not be considered lost to follow-up until just prior to database lock and after all efforts to contact the subject have been exhausted.

If a subject withdraws from study for any reason above, vital status as of Day 374 may be obtained through public registries as permitted by local regulations.

Subjects who wish to withdraw consent from the study, to the extent possible, will undergo an End of Study evaluation equivalent to Visit 8 (Day 374) (see Table 1).

The appropriate case report forms (eCRFs) should be completed, including an explanation as to why the subject participation in the study is being discontinued. Subjects who do not complete the study will not be replaced.

The Investigator and Cirius Therapeutics, Inc. have the right to discontinue study drug dosing from any subject in the event of an intercurrent illness, AE, protocol violation, or other reason including, but not limited to:

- Need for any treatment not allowed by the protocol
- Subject's inability to comply with protocol-specified procedures
- Sites with serious GCP or quality concerns

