- Adverse event that in the opinion of the Investigator requires discontinuation of study drug
- Development of symptoms of CHF that in the opinion of the Investigator requires immediate treatment.

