6.4 Type 2 Diabetes Mellitus

Refer to subject's healthcare provider for diabetic care; however, note that no change in dose is allowed for GLP1 agonists or SGLT2 inhibitors during the study and these drugs cannot be added as rescue medications during the study if the subject had not been on a previous stable dose of either drug 3 months prior to randomization. Use of PPAR γ agonists (pioglitazone or rosiglitazone) or insulin are prohibited during the study.

Subjects being treated with therapeutic agents for diabetes should be on stable dose(s) of the following antidiabetic medications at least 3 months prior to randomization and for the full duration of the trial: metformin, GLP1 agonists, SGLT2 inhibitors, sulfonylureas and DPP4 inhibitors.

If, during the study, a measurement of HbA1c exceeds 9.5% at two consecutive visits, the following suggested rescue approach may be followed:

1. Start metformin or up-titrate metformin if the subject is already taking it

2. Start a DPP4 inhibitor or uptitrate the DPP4 inhibitor if the subject is already taking a DPP4 inhibitor
3. Start careful titration of a sulfonylurea or titrate sulfonylurea if the subject is already taking it.

If no reversible cause is identified or hyperglycemia persists despite counseling and all permitted co-therapies, subject should be discontinued from study drug, referred for treatment, and continue in the study and complete the required study visits.

If a measurement of fasting plasma glucose (FPG) during the study is lower than 60 mg/dL, an alert will be sent to the investigational site and confirmatory FPG should be performed at the site within 7 days. In case of a symptomatic hypoglycemic event and if the subject is on a sulfonylurea, the sulfonylurea dose should be reduced by 50% or discontinued. Severe hypoglycemia is defined as any hypoglycemia requiring the assistance of a third party, hospitalization or associated with seizures or coma. Refer to [Section 9](#) Adverse Events for reporting instructions.

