3.4 Safety Variables

The tolerability and safety will be assessed using the following endpoints:

- The incidence of treatment-emergent adverse events
- Changes from baseline to each time point in clinical laboratory (hematology, chemistry, urinalysis) values (some of which are also evaluated as efficacy parameters), and the occurrence of clinically significant abnormal changes
- Changes from baseline in vital signs (systolic and diastolic blood pressure, heart rate, weight, and abdominal girth) at each visit, which will also be examined as exploratory efficacy endpoints
- Changes from baseline in quantitative electrocardiogram (ECG) parameters (mean heart rate, PR interval, QRS duration, QT interval, QTcB interval, QTcF interval, RR interval)
- Time to first event of death, adjudicated non-fatal myocardial infarction (MI) or unstable angina (USA) hospitalization, adjudicated hospital admission for heart failure (HF), or adjudicated non-fatal ischemic stroke
- Time to first event of death, adjudicated non-fatal MI or USA hospitalization, adjudicated hospital admission for HF, adjudicated non-fatal ischemic stroke, or adjudicated liver event. A liver event consists of ascites, hepatic encephalopathy, variceal hemorrhage, hepatocellular carcinoma (HCC), or liver transplant
- Incidence of adjudicated severe hypoglycemia events
- Incidence of bone fracture requiring surgery or hospitalization

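### Time-to-event analyses of death, MACE and liver events stop 14 days after last dose, with no companion analysis through the planned follow-up to Day 374

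*SAP*

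**What the plan says.** SAP 3.4 lists the time-to-event safety variables, beginning "Time to first event of death, adjudicated non-fatal myocardial infarction", and states no time limit there. SAP 7.9.6 sets the limit. The MACE analysis is "Time to first MACE through 14 days after last dose of study treatment". The MACE-or-liver composite is likewise to be taken "through 14 days after last dose of study treatment will be analyzed and presented". For the components (death, MI, unstable-angina admission, heart-failure admission, stroke, liver event) it says "Results will be presented through 14 days after last dose of study treatment for" the listed outcomes. The censoring rule is "Subjects without an event will be censored at the earlier of the end of the time period of interest and the last contact date". No other period is specified.

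The same 14-day window defines the safety analysis set in Protocol 11.2 and SAP 5.3.

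Data collection runs longer than that for a subject who stops early:

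- Protocol 6.3 says that refusing study drug is not withdrawal of consent and asks investigators to keep such subjects in the remaining parts of the study.
- Protocol 6.4 says that a subject taken off drug for persistent hyperglycemia should be "referred for treatment, and continue in the study and complete the required study visits". Sections 6.5 and 6.6 also continue visits after certain liver-test and bleeding stops.
- Protocol 9.1 and 9.1.7 run AE and SAE reporting to Visit 8, which Section 6.2.10 places at Day 374.
- For subjects who withdraw or are lost, Protocol 6.3 adds that "vital status as of Day 374 may be obtained through public registries", where local rules permit.

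**The concern.** For a subject who takes drug to Day 360, the 14-day limit costs nothing. It shortens follow-up only for early stoppers, and some of the protocol's stopping reasons are early signs of the outcomes being analysed. Protocol 6.3 names "Development of symptoms of CHF that in the opinion of the Investigator requires immediate treatment", and Section 6.5 stops drug for liver-test rises. Kaplan-Meier and Cox methods assume that censored subjects have the same later risk as those who remain. Censoring shortly after a stop prompted by a precursor can break that assumption.

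What is at stake is the between-arm safety comparison. If one dose leads to more safety-driven stops, and heart-failure admissions, liver events or deaths follow more than 14 days later, the planned estimates would not show them. With few events expected in a trial of 380 subjects (95 per arm), one or two could change the picture.

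**Working it through.** **1. Timeline.** Protocol 10 gives up to 42 days of screening, 360 of treatment and 14 of follow-up. 42 + 360 + 14 = 416 days, as stated, and 360 + 14 = Day 374, as stated. The plan gives no event rate, hazard ratio, power or drug-stop rate for these analyses, so there is no further planned figure to reproduce.

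**2. Follow-up outside the window.** For a subject whose last dose is on day s and who is followed to Day 374, the excluded time is 374 - (s + 14) = 360 - s days.

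| Last dose (day) | Days excluded | Share of 374 days |
|---|---|---|
| 90 | 270 | 72% |
| 180 | 180 | 48% |
| 270 | 90 | 24% |
| 360 | 0 | 0% |

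**3. Where a late event goes.** An event within 14 days of the stop is counted. After that, SAP 7.9.1 lists the AE separately, and SAP 7.9.6 lists deaths with adjudicated cause and no stated window. Neither listing feeds a hazard ratio, a cumulative-risk estimate or a test. By contrast, SAP 7.8.1 and 7.8.2 give the biopsy endpoints a sensitivity analysis on all observed data, including results more than 14 days after last dose.

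**4. Person-time, as a range.** With p the proportion stopping early, the excluded share is p x mean(360 - s) / 374. If stop days are spread evenly over 0 to 360, the mean is 180 days.

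- p = 10%: 0.10 x 180 / 374 = 4.8%
- p = 25%: 0.25 x 180 / 374 = 12.0%

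Both values of p are assumptions. The 10% in Protocol 11.1 is non-completion of the 12-month assessment, not drug discontinuation. The shares are upper figures for each p, because they take every stopper as followed to Day 374.

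**5. Direction of any bias.** Over full follow-up, let f be the share of active-arm events outside the window and g the share of active-arm person-time outside it. Suppose that placebo loses events and person-time in equal proportion. With roughly constant rates, a full-follow-up rate ratio R is seen as about R x (1 - f) / (1 - g). Take R = 2.0 and g = 12.0% as an illustration:

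- f = 10%: 2.0 x 0.90 / 0.88 = 2.05
- f = 25%: 2.0 x 0.75 / 0.88 = 1.70
- f = 50%: 2.0 x 0.50 / 0.88 = 1.14

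The ratio is understated only when f exceeds g, that is, when stoppers have a higher event rate after the window than subjects have within it. If the rate falls once drug is stopped, the 14-day version gives the larger ratio.

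**The case against.** The strongest reply is that this is a consistent on-treatment convention. Protocol 11.2 and SAP 5.3 define it, and the treatment-emergent AE definition, severe hypoglycemia (SAP 7.9.7) and fractures (SAP 7.9.8) use the same limit. That stands. A reader might infer from the unlimited wording of SAP 3.4 that it conflicts with SAP 7.9.6, or that the SAP departs from the protocol. The documents do not support this: SAP 3.4 is a list of variables, and the window comes from the analysis set. Even so, SAP 8 records that adjudication of these events came after the protocol was finalized, and nothing in the protocol window rules out a supplementary analysis.

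A reader might also infer that late events vanish. They do not, because they are listed. A heart-failure admission at or near a symptom-driven stop would fall inside the window. What is missing is a comparison that includes the later events.

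Follow-up of stoppers is incomplete as well. Withdrawal of consent means no further visits or contact, registry vital status is optional and covers death only, and the heart-failure bullet in Protocol 6.3 does not itself say that visits continue. Only the general retention instruction applies there. This limits what can be recovered but does not remove it.

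Finally, these are unpowered safety summaries in a Phase 2 trial with preliminary objectives, and listings will carry much of the interpretation. That sets the priority: a supplementary analysis, not a replacement.

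**Conclusion.** The point holds as a gap. Every comparative time-to-event result for death, MACE, MACE-or-liver event and their components ends 14 days after last dose, and none uses the later follow-up that the protocol tries to collect. The censoring can be informative because some stops arise from precursors of the outcomes.

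A reader might go further and conclude that the planned hazard ratios are biased towards no harm. The documents do not establish that. It requires safety-driven stops to differ by arm and the event rate after the window to be raised, and the plan gives neither stop rates nor event rates. The size is therefore unknown. The excluded share of at most about 5-12% of planned person-time rests on assumed early-stop rates of 10-25%, evenly spread stop days and complete follow-up of stoppers. The primary efficacy analysis and the sample size are unaffected.

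**What to change.** Keep the 14-day analyses in SAP 7.9.6. Add the same Kaplan-Meier, Cox and log-rank analyses from baseline through Day 374 or last contact, regardless of drug stop, for death, MACE, MACE-or-liver event and each component. The existing censoring rule already refers to a period of interest, so only that period needs a second definition. For time to death, use registry vital status where it is obtained, and let a finding of alive extend follow-up in the same way as a finding of dead. This mirrors the all-observed-data analysis that SAP 7.8.1 already gives the biopsy endpoint.

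Confirm that the Clinical Events Committee adjudicates events through Day 374. SAP 7.9.6 does not state the adjudication period.

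The cost is one more run of the same programs, plus adjudication of any late events not yet reviewed. The drawback is that off-drug time may dilute a drug-related hazard, which is why the two versions should be reported side by side.
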